At the Baseline visit (which may be combined with the Screening visit), eligible subjects will be randomized in equal allocation (at a 1:1:1:1:1:1 ratio) to one of the following 6 active treatment groups (5 experimental groups and 1 active comparator group):

- Treatment Group 1: oral SCY-078 750 mg QD on Day 1 only
- Treatment Group 2: oral SCY-078 300 mg BID on Day 1 only
- Treatment Group 3: oral SCY-078 450 mg BID on Day 1 only
- Treatment Group 4: oral SCY-078 150 mg BID on Days 1 to 3
- Treatment Group 5: oral SCY-078 300 mg BID on Days 1 to 3
- Treatment Group 6: oral fluconazole 150 mg QD on Day 1 only

Subjects will receive randomized treatment from Day 1 through Day 3. For the purpose of maintaining treatment blinding, all randomized subjects will receive matching SCY-078 placebo tablets and/or matching fluconazole placebo capsules as needed based on treatment assignment, in a double-dummy fashion. During treatment days, subjects will rate their vulvovaginal symptoms and record dosing details, AEs and concomitant medication use daily on subject diaries. On Day 3, a PK Subset consisting of 10 subjects per treatment group (total of 60 subjects) will visit the site to have PK samples drawn pre-dose (immediately before dosing) and at 2-6 hours' post-dose of either the morning or evening dose. Day 3 will be an on-site visit for PK

subjects and a phone contact visit (with a window of +3 days) for non-PK subjects. All subjects (both PK and non-PK subjects) will continue to take their assigned study treatment and rate their symptoms of infection within their subject diaries. Treatment compliance will be reviewed either on site or by phone for all subjects. Study drug may be collected from PK subjects who have completed study drug dosing at the time of this visit.

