The concentration versus time data from the PK samples collected in this study will be analyzed using a Pop PK model to predict AUC and C_{max} (as appropriate). A Pop PK modeling strategy is required because the sampling time points will not support a standalone PK analysis, and hence, the data from this study will be pooled with data from other oral studies to predict AUC and C_{max} on Day 1 of treatment. A stand-alone Population PK report will be prepared to describe the analysis performed on the PK samples collected from this study.

Further analysis of possible metabolites may be performed.

Efficacy Analyses

The efficacy analyses will be conducted using the mITT (primary analysis population), ITT and PP populations. The efficacy parameters will be evaluated comparing each SCY-078 treatment group (and all treatment groups combined) versus the active comparator (fluconazole) group.

The primary endpoint (clinical cure at TOC) will be analyzed using a Cochran-Mantel-Haenszel row mean scores test. Pairwise treatment comparisons of SCY-078 vs. fluconazole will be performed using a Fisher's Exact test; p-values and 95% confidence intervals will be presented. Subjects whose results are missing at Day 10 (TOC) will be imputed as failures in the analysis. A sensitivity analysis will be performed where subjects with missing values will be removed from the analysis.

For continuous efficacy endpoints, the Student's t-test will be used for pairwise treatment comparisons of SCY-078 vs. fluconazole; p-values and 95% confidence intervals will be presented for the differences between treatment groups. For categorical endpoints, Fisher's Exact test will be performed, and p-values and 95% confidence intervals will be presented. The time to resolution of signs and symptoms after initiation of study drug will be analyzed using Kaplan-Meier methods.

Safety Analyses

Safety analyses will be conducted using the safety population.

AEs will be coded using the Medical Dictionary for Regulatory Activities (MedDRA) Version 19.1 or higher. The incidence and severity of treatment-emergent AEs and SAEs and their relationship to treatment will be summarized by system organ class and preferred term. The percentage of subjects who discontinued study treatment and the reasons for discontinuation will be summarized by treatment group.

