7.2 Rationale for the Study

This study is being performed to evaluate the efficacy and safety of different dose levels and dosing regimens of SCY-078 as compared to fluconazole in adult female patients 18 years and older with moderate to severe AVVC.

Rationale for Study Indication and Population

Considering the properties of SCY-078 as a potent antifungal compound, with fungicidal activity against *Candida* spp., it will represent an important non-azole alternative treatment for subjects suffering from AVVC.

Subjects with moderate to severe AVVC are intended for this study to facilitate the identification of a clinically meaningful effect of SCY-078 with a limited sample size.

Rationale for Selected Dose Levels and Dosing Regimens

The SCY-078 dose levels and dosing regimens selected for this study (750 mg QD for 1 day, 300 mg twice daily [BID] for 1 day [total daily dose of 600 mg], 450 mg BID for 1 day [total daily

dose of 900 mg], 150 mg BID for 3 days [total daily dose of 300 mg] or 300 mg BID for 3 days [total daily dose of 600 mg]) are in the range of doses that have been well tolerated in Phase 1 investigations. Since the estimated effective exposure of SCY-078 for vulvovaginal candidiasis has not been determined, this study will contribute to a better understanding of the exposures that may be associated with clinical efficacy for this indication to guide further investigations.

The dose selected for the active comparator of this study (fluconazole) is one single oral dose of 150 mg, which is the recommended and approved dose for this indication.

Rationale for Study Endpoints

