9.3 Exploratory Endpoints

- Percentage of subjects with a negative KOH test at the TOC visit
- Percentage of subjects who are free of signs and symptoms at the FU visit
- Percentage of subjects by *Candida* species infection at Baseline
- Percentage of isolates susceptible to SCY-078 and fluconazole
- Percentage of subjects with clinical cure (complete resolution of signs and symptoms) at TOC by *Candida* species
- Percentage of subjects with mycological eradication (negative fungal culture) at TOC by *Candida* species
- Determination of the PK parameters (C_{max} and AUC) for each dosing regimen and evaluation of the dose/exposure relationship relative to clinical outcome

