18.6.2 Pharmacokinetic Analyses

PK parameters will be estimated using Population PK analysis in NONMEM as detailed in the SAP. The PK analyses will be done using the PK Population.

An evaluation of exposure for each dosing regimen relative to clinical cure will be performed.

The concentration versus time data from the PK samples collected in this study will be analyzed using a Population PK (Pop PK) model to predict AUC and C_{\max} (as appropriate). A Pop PK modeling strategy is required because the sampling time points will not support a standalone PK analysis, and hence, the data from this study will be pooled with data from other oral studies to predict AUC and C_{\max} on Day 1 of treatment. A stand-alone Population PK report will be prepared to describe the analysis performed on the PK samples collected from this study.

Further analysis of possible metabolites may be performed.

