3A4	
In vitro, SCY-078 was an inhibitor of CYP3A mediated metabolism of midazolam, but was only a weak inhibitor of metabolism of testosterone. The clinical significance of this inhibition is unknown; caution should be exercised when administering SCY-078 with drugs known to be CYP3A sensitive substrates with narrow therapeutic index.
 
Subjects receiving sirolimus, tacrolimus or warfarin are permitted for enrollment in the study and these medications may be administered concomitantly with SCY-078 with close monitoring. The administration of either sirolimus or tacrolimus should be offset by no less than 2 hours with the administration of SCY-078. At a minimum, blood levels of sirolimus, tacrolimus or PT/PTT/INR for subjects on warfarin should be measured after the first dose of SCY-078 and when the subject has received approximately 7 days of SCY-078 (at which time, SCY-078 concentrations will have reached steady state). Dosing adjustments and subsequent monitoring of sirolimus and warfarin should be undertaken in accordance with product prescribing information for the respective agents.

Abbreviations: PT = prothrombin time; PTT = partial thromboplastin time; INR = international normalized ration

OATP1B3 substrates

OATP	Substrate
1B3	
In vitro, SCY-078 is an inhibitor of the OATP1B3 liver uptake transporter. The clinical significance of this inhibition is unknown; however, there is a potential risk for increased exposure of the concomitant medications (arising from lowered hepatic clearance) when administering SCY-078 with drugs known to be OATP1B3 selective substrates. Therefore, caution should be exercised when administering SCY-078 with drugs known to be OATP1B3 selective substrates such as telmisartan, including monitoring the subject for signs of overexposure associated with the concomitant medications as described in the product prescribing information.

Sources:

- FDA Draft Guidance for Industry. Drug Interaction Studies – Study Design, Data Analysis, and Implications for Dosing and Labeling. 2012.
- Drug interactions in infectious disease by Stephen C. Piscitelli, Keith Rodvold (2007)
- UCSF-FDA Transportal

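### Day 1 is the only interval named for predicted exposure, and on it the 1-day and 3-day 300 mg BID regimens cannot be told apart in the exposure-cure evaluation

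*Protocol*

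**What the plan says.** The population PK text appears in the Protocol synopsis (Pharmacokinetic Analyses) and again in section 18.6.2. Because sampling is too sparse for a standalone analysis, the data are to be "pooled with data from other oral studies to predict AUC and C_{max} on Day 1 of treatment". Section 18.6.2 gives the use: "An evaluation of exposure for each dosing regimen relative to clinical cure will be performed". The exploratory endpoint in section 9.3 is Cmax and AUC "for each dosing regimen and evaluation of the dose/exposure relationship relative to clinical outcome", with no interval attached. Section 7.2 says that the effective exposure for this indication is unknown and that the study should give a "better understanding of the exposures that may be associated with clinical efficacy".

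Three regimens dose on Day 1 only (Groups 1, 2 and 3). Groups 4 and 5 take 150 mg BID and 300 mg BID on Days 1 to 3 (Protocol 12.0, Table 1). PK samples are drawn on Day 3 and Day 10, from 10 subjects per group.

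The protocol refers to the SAP for detail. SAP 11.11 names no exposure metric and leaves PK to a separate vendor report tied to database lock. SAP section 5 places unblinding at database closure.

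**The concern.** The design varies both dose and duration. The pair "Treatment Group 2: oral SCY-078 300 mg BID on Day 1 only" and Group 5 (300 mg BID on Days 1 to 3) isolates duration at a fixed dose. A Day 1 exposure metric stops before the two regimens diverge. Any difference in cure between them would then appear at equal typical exposure, as unexplained variation. Likewise, a good result in Group 4 would appear as high cure at the lowest exposure.

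At stake is the exploratory exposure-cure relation, which section 7.2 says is to guide later work. A target read from Day 1 exposure alone could mislead if duration matters. And because no reviewed document fixes another metric, one could be chosen after the cure results are known.

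**Working it through.** **1. Doses, from Protocol Table 1, checked against section 12.3.2.** Day 1 dose = dose level × doses per day. Course dose = Day 1 dose × dosing days. The Day 1 doses reproduce Table 1's total daily doses (750, 600, 900, 300, 600 mg).

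| Group | Day 1 dose | Course dose | Tablet check |
|---|---|---|---|
| 1 | 750 × 1 = 750 mg | 750 × 1 = 750 mg | 5 × 150 = 750 |
| 2 | 300 × 2 = 600 mg | 600 × 1 = 600 mg | 4 × 150 = 600 |
| 3 | 450 × 2 = 900 mg | 900 × 1 = 900 mg | 6 × 150 = 900 |
| 4 | 150 × 2 = 300 mg | 300 × 3 = 900 mg | 6 × 150 = 900 |
| 5 | 300 × 2 = 600 mg | 600 × 3 = 1800 mg | 12 × 150 = 1800 |

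**2. Rankings by dose alone.**
- Day 1: G3 900 > G1 750 > G2 = G5 600 > G4 300.
- Course: G5 1800 > G3 = G4 900 > G1 750 > G2 600.
- Of the 10 pairs, 4 keep their order, 4 reverse (G1–G4, G1–G5, G2–G4, G3–G5) and 2 are tied in one ranking (G2–G5, G3–G4). Kendall tau is 0.00 and Spearman rho is −0.11.

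The G2 = G5 tie needs no PK assumption: dose and timing on Day 1 are identical.

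**3. Illustrative model.** The documents give no half-life or absorption rate, so these are assumptions: one compartment, linear, first-order absorption. With k = ln 2 / half-life and u = hours from a dose D to the end of the window, that dose contributes to CL × AUC

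D × [1 − (ka·e^(−k·u) − k·e^(−ka·u)) / (ka − k)].

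Appendix A refers to "approximately 7 days of SCY-078 (at which time, SCY-078 concentrations will have reached steady state". Reading 7 days as 5 half-lives gives 168 / 5 = 33.6, about 34 h; reading it as 4 gives 42 h. The note says when steady state will have been reached, so shorter half-lives also fit it.

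Group 2 at 34 h and ka 0.5/h (k = 0.0204): the first dose gives 300 × 0.361 = 108 and the second 300 × 0.184 = 55, together 163 mg-equivalents. Group 5 has the same 163. Groups 1, 3 and 4 give 271, 245 and 82.

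**4. Share of course exposure falling in the first 24 h** (24-h value / course dose; for example 163 / 600 = 27% in Group 2 and 163 / 1800 = 9% in Group 5).

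| Half-life (ka 0.3 to 50/h) | Groups 1–3 | Groups 4–5 |
|---|---|---|
| 10 h | 60–81% | 20–23% |
| 20 h | 38–56% | 13–15% |
| 34 h | 25–39% | 8–10% |
| 42 h | 21–33% | 7–8% |

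Over this grid, the Spearman correlation between Day 1 AUC and course exposure is −0.11 to −0.26.

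**5. What a longer window shows** (half-life 6 to 48 h, ka 0.3 and 1.0/h, relative to Group 2).

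| Metric | G5 : G2 | G4 : G2 |
|---|---|---|
| Day 1 AUC and Day 1 Cmax | 1.00 | 0.50 |
| AUC0–72 | 2.0–2.8 | 1.02–1.41 |
| AUC0–inf | 3.0 | 1.50 |
| Cmax over the course | 1.1–2.3 | 0.54–1.15 |

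Group 5 is first on AUC0–72 and AUC0–inf in every scenario, against tied third on Day 1 AUC.

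**The case against.** The strongest reply is that the protocol does not confine the analysis to Day 1. Both PK sections first say that AUC and Cmax will be predicted as appropriate, without a day. The endpoint in section 9.3 has no interval, the sentence relating exposure to cure does not mention Day 1, and the population PK report may add metrics. This stands: Day 1 is the only interval named, but a reader who infers that no other will be used goes beyond the text.

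Second, a reader might infer that Day 1 exposure puts the regimens in the wrong order, or reverses the exposure-cure slope. That assumes cumulative exposure drives cure. Section 7.2 says the effective exposure is undetermined, and early or peak exposure could be what matters. The low correlations show that two metrics differ, not which is right. No cure model has been fitted or simulated here. Comparing 1-day with 3-day regimens allows that duration may matter; it does not establish it.

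Third, a reader might infer from Appendix A that Day 1 misses most of the exposure from Day 1 dosing. That depends on the half-life: at 10 h, Day 1 captures 60–81% in Groups 1–3.

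Fourth, a whole-course metric has its own blind spot. Under linear PK, AUC0–inf ties Groups 3 and 4 at 900 mg. This is a reason to keep the Day 1 metrics, not replace them.

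Fifth, the analysis is exploratory, in about 50 SCY-078 subjects (5 × 10), and results are presented by treatment group, so a duration effect would still show in the cure rates. This limits the weight of the point but does not supply the missing metric. Individual model estimates will also differ within Groups 2 and 5; the tie concerns typical exposure.

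**Conclusion.** The point holds as a gap in specification. The one interval named for predicted exposure cannot separate Group 2 from Group 5, a threefold difference in course dose (1800 / 600), and it places Group 4 lowest although its course dose equals Group 3's. The first statement rests only on the dosing table; the second needs only that exposure rises with dose.

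Whether this distorts the exposure-cure relation is conditional on exposure after Day 1 contributing to cure at Day 10, which the documents leave open. The capture figures rest on an assumed linear model and should be quoted only as a range: about 21–81% in Groups 1–3 for half-lives of 42 down to 10 h.

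The primary objective is pursued by comparing cure between randomized groups, and that comparison is untouched. This is a low-cost improvement to an exploratory analysis, worth making before unblinding because neither document fixes a whole-course metric.

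**What to change.** In the Protocol synopsis and section 18.6.2, and in a PK analysis plan finalized before unblinding, pre-specify two sets of individual predicted metrics:
- Day 1 AUC and Cmax, as now;
- a whole-course AUC (cumulative from first dose to TOC, or AUC0–72) and Cmax over the treatment period.

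Report exposure versus clinical cure for both sets, and have SAP 11.11 refer to that plan. AUC0–72 has the advantage of not tying Groups 3 and 4: relative to Group 2 they are at 1.50 and 1.02–1.41 over the range tried.

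The cost is wording and one further AUC and Cmax derivation from the same model and samples; no visit or blood draw is added. The drawback is that the cumulative AUC relies on the model's terminal phase, so the report should state how well the Day 3 and Day 10 samples and the pooled data support it.

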6.0 Schematic of Study Design

[figure not shown]

Figure 1 Schematic of Study Design

7.0 Background Information and Scientific Rationale

7.1 Background Information

Vulvovaginal Candidiasis

Vulvovaginal candidiasis (VVC) is a common fungal infection caused by *Candida* spp and is a significant morbidity condition in women from all social classes.

Information on the incidence of VVC is incomplete, since the disease is not a reportable entity and data collection is hampered by inaccuracies of diagnosis and the use of non-representative study populations.¹ VVC affects 70%–75% of women at least once during their lives, most frequently young women of childbearing age. Approximately 40%–50% of women will experience a recurrence² and 5% to 8% of adult women have a recurrent vulvovaginal candidiasis.³ The reported incidence goes from 15% to 30%.^{4,5}

Current treatments for VVC include topical antifungals and the use of prescription oral antifungals such a single doses of fluconazole. In two vaginal candidiasis studies conducted with fluconazole, the therapeutic cure rate, defined as the resolution of signs and symptoms of vaginal candidiasis along with negative KOH examination and negative culture for *Candida*, was achieved by 55% of subjects receiving single doses of fluconazole 150 mg. The therapeutic cure rate is reduced to 40% in subjects with a history of recurrent vaginitis.^{6,8} Although a single dose of fluconazole is able to provide an acceptable therapeutic outcome for more than half of the treated individuals, the emergence of fluconazole resistance among *C. albicans* isolates and the frequency of cases caused by *C. glabrata*, a strain naturally less susceptible to fluconazole, signals the need for new therapeutic approaches.

Additionally, recurrence of VVC after fluconazole therapy is not uncommon and these exacerbations often involve the same microorganism identified in the initial episode, suggesting that a small number of *C. albicans* remain as a reservoir in the vagina after completion of azole therapy, becoming the source of subsequent exacerbations. This may be explained by the fact that azoles are fungistatic, which means that they slow the growth of, but do not kill, the fungus and azoles are not active against certain species of *Candida* that cause VVC.

New curative approaches are needed, particularly involving agents with fungicidal activity (i.e., that are able to kill the fungus) and activity against fluconazole-resistant strains, so that the causative yeasts can be eradicated. A new therapeutic approach with these characteristics would be expected to result in improved short-term and potentially long-term outcomes for this condition.

This study aims to identify the efficacious dose of SCY-078, as a new class of antifungal agent with fungicidal activity against *Candida* spp. in the treatment of patients with VVC.

The glucan synthesis inhibitor SCY-078

SCY-078 is a member of a new class of antifungal agents and is an orally active, semi-synthetic, triterpene derivative of the natural product enfumafungin. SCY-078 is a structurally distinct class of glucan synthesis inhibitor (GSI) that inhibits the synthesis of the fungal cell wall polymer β -

(1,3)-D-glucan. Time-kill studies have demonstrated that SCY-078 has *in vitro* fungicidal activity against *Candida* spp. isolates similar to that observed with the echinocandins.

SCY-078 is being developed as the first oral and intravenous (IV) GSI for the treatment and prevention of fungal infections caused by *Candida* and *Aspergillus* species with the potential to provide the therapeutic advantages of both an IV and oral formulation.

Antifungal activity

The spectrum and potency of activity of SCY-078 has been evaluated by numerous independent laboratories against an extensive panel of clinically relevant yeast and mold isolates using the Clinical and Laboratory Standards Institute (M27-A3 guidelines)⁷ and European Committee on Antimicrobial Susceptibility Testing methods. Overall, the epidemiological studies have demonstrated that SCY-078 has potent, broad-spectrum activity against the majority of the clinical isolates tested. These studies have laid the foundation in support of the use of SCY-078 for the treatment of invasive fungal infections.

Activity against *Candida* spp.

SCY-078 has been evaluated against >1200 *Candida* isolates, including all clinically relevant species, more than 300 *C. glabrata* isolates and 16 *C. auris* isolates. These *in vitro* studies have demonstrated the broad spectrum of anti-*Candida* activity of SCY-078. Additionally, SCY-078 demonstrated *in vitro* activity against pre-formed biofilms, which is a relevant feature when addressing catheter-related *Candida* infections. Studies conducted with azole- and echinocandin-resistant strains have shown that SCY-078 retains activity (i.e., no significant change in minimum inhibitory concentration when compared to wild type) against >90% of azole-resistant strains and >70% of *Candida* strains with *FKS* mutations commonly associated with echinocandin resistance. Interestingly, although SCY-078 and the echinocandins share a similar mechanism of action (β -[1,3]-D-glucan synthesis inhibition), their clearly different molecular structure provides them with some differentiating characteristics in terms of microbiological activity.

SCY-078 was evaluated *in vitro* against >170 clinical isolates of echinocandin-resistant strains of *Candida* spp., >95% of which contained mutations in the *FKS* gene. Overall, SCY-078 was active against the majority of the echinocandin-resistant strains tested. Significantly, SCY-078 was active against approximately 70% of the isolates containing the most commonly reported *FKS* mutation associated with echinocandin resistance in *C. glabrata* (S663P in *FKS2* and S645P in *FKS1*). Selection of SCY-078 resistance *in vitro* occurs at a low frequency. A deletion at position F659 in *FKS2* of *C. glabrata* was the predominant mutation observed in these studies; notably, SCY-078 did not select for mutations at positions S663 or S645. These results suggest that SCY-078 inhibits glucan synthase in a manner different from that of echinocandins.

The *in vitro* studies also included several multidrug-resistant isolates. Consistent with the data described above, SCY-078 was active against >70% of these isolates. SCY-078 has also demonstrated a potent activity against life-threatening and multi-drug-resistant *C. auris* strains

over 16 different *C. auris* isolates, at concentrations indicative of potential clinically relevant effect.⁷ *C. auris* has been recently highlighted as a clinical alert by the CDC because of the global emergence of this fungal infection with limited therapeutic options and high mortality.

Activity against *Aspergillus* spp.

The *in vitro* activity of SCY-078 has been evaluated against >150 clinical *Aspergillus* isolates, including most clinically relevant species and azole-resistant strains. The results demonstrated potent activity of SCY-078 against all of the strains tested.

Murine models of invasive fungal infections

The antifungal efficacy of SCY-078 has been evaluated in several murine models of disseminated candidiasis and aspergillosis. In a disseminated *C. albicans* model, SCY-078 was more active than fluconazole at all doses. Murine models of SCY-078 in disseminated candidiasis caused by *C. glabrata* and *C. tropicalis* indicated activity across multiple *Candida* species. The SCY-078 area under the concentration-time curve (AUC) in plasma necessary to achieve target efficacy in these models was estimated to be $15.4 \pm 2.2 \mu\text{M}\cdot\text{hr}$.

Nonclinical experience

Toxicology studies in rats and dogs have been conducted with SCY-078 following oral administration for up to 90 days. The results from the non-clinical safety program are supportive of the doses and treatment duration intended in this study.

The *in vitro* studies indicated that SCY-078 metabolism was predominantly oxidative, with cytochrome P450 (CYP) 3A being the primary enzyme involved in its oxidative metabolism. Strong inhibitors of CYP3A would be expected to increase plasma levels of SCY-078; therefore, the concurrent administration of SCY-078 with such inhibitors is prohibited.

Clinical experience

To date, over 300 subjects and patients have received either oral or IV formulations of SCY-078 in Phase 1 and Phase 2 studies.

SCY-078 was generally well tolerated following single oral doses of up to 1600 mg and multiple oral doses of up to 800 mg/day for 28 consecutive days in Phase 1 studies. Reported adverse events (AEs) after oral administration have been generally transient and primarily mild to moderate in intensity. The most frequently reported AEs have been mild gastrointestinal events (nausea, vomiting, diarrhea and abdominal pain).

A Phase 2 study of oral SCY-078 as step-down therapy from IV echinocandin in patients with invasive candidiasis has been completed. Following three to ten days of IV echinocandin therapy, 21 patients received either SCY-078 or fluconazole. SCY-078 was well tolerated, with an AE profile typical of this population and comparable to the SOC. The results from this study also

indicated that the higher dose of SCY-078 tested (750 mg QD) is predicted to achieve the target exposure at steady state in the majority of patients.

A Phase 2 proof-of-concept study of oral SCY-078 in patients with acute vulvovaginal candidiasis (AVVC) has also been completed. In this multicenter, randomized, active-controlled, evaluator-blinded study of oral SCY-078 compared to oral fluconazole in adult female patients with AVVC, 96 patients with an acute, moderate to severe, symptomatic episode of vulvovaginal candidiasis were randomized in a 1:1:1 ratio to receive either oral SCY-078 750 mg with a 1250 mg loading dose for three days, oral SCY-078 750 mg with a 1250 mg loading dose for five days or a single dose of oral fluconazole. SCY-078 was well tolerated, with the most common AEs being mild gastrointestinal events. The high clinical cure rates observed in this study are supportive of the clinically relevant antifungal activity of SCY-078 in this form of *Candida* infection.

Several drug-drug interaction studies have been conducted. Ketoconazole (a strong inhibitor of CYP3A) induces a significant (5-fold) increase in SCY-078 exposure, while diltiazem (a moderate inhibitor of CYP3A) induces a mild to moderate (<3-fold) increase in SCY-078 exposure. SCY-078 did not have any effect on rosiglitazone (a CYP2C8 substrate) exposure, had only a mild effect (less than a 0.5-fold increase) on the AUC of tacrolimus (a CYP3A and P-glycoprotein [P-gp] substrate) and had no effect on the maximum concentration (C_{max}) of tacrolimus.

SCY-078 has the potential to be an important addition to the antifungal treatment arsenal by providing potent activity against the full spectrum of *Candida* species, including difficult-to-treat organisms, and by affording the added flexibility of both oral and IV formulations.

For additional information on SCY-078, please refer to the Investigator's Brochure (IB).

